1. For participants who report being in a relationship, what is the impact of the on-demand delivery (treatment) compared to the in-person delivery (counterfactual) of the TYRO Couples curriculum on **marriage/intimate partner relationship behaviors** six months after program enrollment?
2. For participants who report being in a relationship, what is the impact of the on-demand delivery

¹ Source: Chou, S., & Liu, C. (2005). Learning effectiveness in a web-based virtual learning environment: A learner-control perspective. *Journal of Computer Assisted Learning*, 21(1), 65 - 76.

(treatment) compared to the standard in-person delivery (counterfactual) of the TYRO Couples curriculum on **marriage/intimate partner relationship attitudes** after program completion?

3. Primary and secondary outcome measures

For this impact evaluation study, the intervention that will be tested is the delivery format of the TYRO Couples curriculum. The research questions are framed to determine if program participants who are randomly assigned to the TYRO Couples curriculum through an on-demand format will derive more benefits compared to those who are assigned to the TYRO Couples curriculum in a standard, in-person format.

Primary research questions are applicable to the entire population in the study and will be measured six months after the intervention has ended. This study focuses on employment and financial attitudes as the primary research questions. Finding and maintaining a job, which is one of the top priorities participants will have after release, has been noted in criminal justice research to reduce former prisoners' chances of reoffending (Visher, Debus, and Yahner, 2008). Subsequent secondary research questions focusing on relationships are only applicable to the study population who report being in a relationship. However, all research questions are relevant to the TYRO Couples Curriculum as well as consistent with the study's logic model.

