The data for this impact evaluation comes from surveys of study participants. Participants are surveyed at three different time points throughout the study-baseline, post-survey, and six-month post-enrollment follow-up. The process and timing for data collection are the same for all study participants, regardless of study condition assignment. Wave 1 of data collection, which includes completion of the nFORM Applicant Characteristics Survey, the nFORM Healthy Marriage Adult Program Entrance Survey, and the local evaluation baseline survey, happens during orientation before any primary workshop hours have been delivered. Wave 2 of data collection, which includes the nFORM Healthy Marriage Adult Program Exit Survey and the local evaluation post-survey, happens six weeks after program enrollment for both study groups. Wave 2 of data collection happens immediately following the final primary workshop session for the in-person group, but since the on-demand mode is self-paced, the amount of time that has elapsed between curriculum completion and wave 2 of data collection six weeks post-enrollment can vary for on-demand group participants. For example, if a participant in the on-demand delivery group completes the TYRO curriculum two weeks after enrollment, then four weeks will have elapsed between program completion and administration of the exit survey.

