Each of the outcomes for the primary research questions for this study are constructed averages using multiple, related survey items. Sufficiently high item nonresponse among items used to construct outcome measures will lead to sample attrition for that outcome. The evaluation team plans to use an 80% threshold as the cutoff for constructed measures; respondents who answer less than 80% of survey items associated with a constructed measure will be dropped from the analysis for that outcome. The constructed average for each participant who has answered at least 80% of associated survey items will be calculated by dividing the sum of their survey answers by the number of items they answered. For example, if a participant answers 8 out of 10 survey items associated with a construct, their average for that outcome measure will be the sum of their 8 answers divided by 8. The evaluation team does not plan to use imputation for multi-item constructed outcomes with 20 percent or fewer missing items. A sensitivity analysis will be conducted to see if and how results would change with a 70% threshold cutoff instead of an 80% cutoff.

2. Attrition and analytic sample

The analytic sample for each outcome construct identified in Table 2 will consist of study participants who have a non-missing value at baseline and follow-up time points for that construct (complete case). The size of the analytic sample may vary by outcome measure based on the prevalence of item non-response missing data at the baseline and follow-up surveys for the items used to create those composite measures. For attitudinal outcomes related to economic stability, and finances, all respondents with complete case data will be included in the analytic sample. For relationship behavior outcomes, participants will be included in the analytic sample if they report being in a committed relationship at the time the survey was administered (i.e., do not choose 'no' for the skip logic question 'Are you currently in a committed romantic relationship?'). Because this skip logic was added to the local evaluation surveys belatedly (in October 2023), this condition will only apply to those respondents who took a survey with this skip logic. For those respondents who took a survey before this relationship skip logic was added, all participants who have complete case data will be included in the analytic sample in response to the secondary research question.

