Analyses will be conducted using the R Studio statistical software package. The basic model for this impact evaluation will include a dummy variable for intervention group assignment, equal to 1 if a participant was randomly assigned to receive the curriculum on-demand via tablet, and a participant's score at baseline as the main predictors of each outcome measure at follow-up. To enhance the precision of the impact estimates, we plan to include several other covariates in our models. For all outcome analyses, we will control for participant age, gender, and race, as well as the timing of a participant's follow-up survey (number of days between program enrollment and follow-up survey completion). We will also consider including a facility indicator to denote which site the participant received services at. Additionally, we will include any demographic variables that were shown to be significantly different between study groups during baseline equivalency analysis. For the healthy relationship attitudes outcome, we also plan to include relationship status at baseline as a covariate. This will only be available if a participant reports being in a relationship at baseline and at follow-up.

Table 6. Covariates included in impact analyses

Covariate	Description of the covariate
Age	Age (in years) as of the baseline data collection, as reported on the ACS
Gender	Self-reported gender identification as of the baseline data collection, as reported on the ACS
Race	Self-reported racial identification as of the baseline data collection, as reported on the ACS

Covariate	Description of the covariate
Timing of follow-up survey	Number of days between program enrollment date and date of follow-up survey completion to control for variation in survey timing
Relationship status (relationship attitude and behavior outcomes only)	Relationship status (1 = in a committed relationship, 0 = not in a committed relationship) as of the baseline data collection, as reported on the ACS

4. Sensitivity analyses for primary research questions

We plan to conduct several sensitivity analyses to test the robustness of our results. First, and as mentioned earlier in the plan, we will conduct a sensitivity analysis to see if and how our outcome construct measures change if we use 70% as a threshold for non-missing items instead of 80% as a threshold.

[figure not shown]

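### The secondary relationship analyses admit respondents surveyed before October 2023 without a relationship check, and the six-week Relationship Attitudes outcome is tied to the six-month survey

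*Combined protocol and SAP*

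**What the plan says.** **Population.** Section A.2 opens both secondary questions the same way: "For participants who report being in a relationship, what is the impact of the on-demand delivery". Section A.1 calls these outcomes exploratory and expects them to be underpowered.

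**Analytic sample.** Section D.2 requires participants to "have a non-missing value at baseline and follow-up time points for that construct". For relationship behavior outcomes it adds that "participants will be included in the analytic sample if they report being in a committed relationship at the time the survey was administered". That condition applies only to surveys carrying the skip logic added in October 2023. For earlier surveys, "all participants who have complete case data will be included in the analytic sample in response to the secondary research question". The Table 2 note, section D.1 and Figure A.4 show that the skip logic covers the Attitudes items as well as the Behaviors items.

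**Covariates.** Section D.3 plans baseline relationship status as a covariate for Attitudes and then says: "This will only be available if a participant reports being in a relationship at baseline and at follow-up". Table 6 takes the same covariate from the ACS, codes it "1 = in a committed relationship, 0 = not in a committed relationship" and lists it for both relationship outcomes. All outcome models also include the "number of days between program enrollment and follow-up survey completion".

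**Timing.** Table 2 takes Relationship Attitudes from the post-survey. Section C.2 treats the post-survey as a separate wave from the six-month follow-up and says that it "happens six weeks after program enrollment for both study groups". Section A.3 defines change scores for composites from pre-program to six months. Section D.1 (Survey nonresponse) removes follow-up nonrespondents from the analytic sample.

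**The concern.** The sample rule does not match the question. Whether someone without a partner is analysed depends on which version of the survey they happened to take. Later respondents are selected on their status when surveyed, which at the outcome wave is after randomisation.

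Complete-case status is not a reliable substitute for a relationship check. Section B.2 reports that over half of those answering the ACS item had no current partner, whereas section D.1 reports only 25-28% of relationship responses missing.

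The covariate descriptions in D.3 and Table 6 cannot both govern. One makes availability depend on status at follow-up; the other is a baseline variable known for everyone who answered the ACS item.

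For Attitudes, the timing covariate is measured months after the outcome and does not describe when that outcome was taken. It also does not exist for someone who never answers the six-month survey, so a complete-case model would lose that person even with a usable six-week score.

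Left as it is, the analyst would have to choose among samples and covariates after seeing data.

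**Working it through.** The plan gives no figure of its own to reproduce here. The check sizes the early group and then the possible share without a partner.

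**Step 1: how many surveys precede the switch.** Inputs: main-cohort enrollment April 11, 2023 to November 30, 2024 (Table 5, Wave 1), which is 600 days counted inclusively; a switch between October 1 and October 31, 2023; even enrollment (assumed).

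- Post-survey at 42 days: 131 to 161 enrollment days give a survey before the switch. 131/600 = 21.8%; 161/600 = 26.8%.
- Follow-up at 183 days: 0 to 20 days. 0/600 = 0%; 20/600 = 3.3%.

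The pilot cohort (January 2023 baseline in Table 5) is left out because its size is not given. Its six-month surveys would fall around July 2023, and Figure A.3 dates follow-up collection from July 1, 2023. Some Behaviors follow-ups therefore precede the switch, although Table 5 starts Wave 3 only in October 2023, and in May 2024 for Franklin CBCF (about 78% of participants).

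**Step 2: does answering the items imply having a partner?** Take 50% without a partner (B.2 says over 50%) and m = 0.25 to 0.28 missing (D.1), read as a person-level rate before the skip logic. If every missing response came from someone without a partner, the share without a partner among those answering one early survey is (0.50 - m)/(1 - m):

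- m = 0.28: 0.22/0.72 = 30.6%
- m = 0.25: 0.25/0.75 = 33.3%

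**Step 3: share without a partner in the scored Attitudes sample.** A scored case needs a baseline and an outcome value. Let e be the early share, x the fraction of early respondents who have no partner and are scored, y the fraction of early respondents who are scored, and a the fraction answering the new version. Here a runs from 0.29 (romantically involved or committed, B.2) to 0.50 (everyone with a partner).

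Share = e·x / [e·y + (1 - e)·a]

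The low end uses e = 0.218, m = 0.28, a = 0.50. The high end uses e = 0.268, m = 0.25, a = 0.29.

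| Missingness assumption | x | y | Low | High |
|---|---|---|---|---|
| Only people without a partner; different people at each wave | 0 | 0.50 | 0% | 0% |
| Only people without a partner; independent between waves | 0.5(1 - 2m)² | 0.5 + x | 0.0211/0.521 = 4.0% | 0.0335/0.380 = 8.8% |
| Only people without a partner; same people at both waves | 0.50 - m | 1 - m | 0.0480/0.548 = 8.8% | 0.0670/0.413 = 16.2% |
| Unrelated to partner status; same people at both waves | 0.5(1 - m) | 1 - m | 0.0785/0.548 = 14.3% | 0.1005/0.413 = 24.3% |

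In the first row, 2m is at least 0.50, so missingness at the two waves can remove everyone without a partner. All rows assume equal survey completion across versions and no change in status.

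**Step 4: the timing rules for Attitudes, side by side.** The D.3 timing covariate names the follow-up survey and applies to every outcome, so the conflict is direct. The A.3 change score names six months, which is also a direct conflict, although the D.3 model regresses the later score on baseline and may never use it. The D.2 sample rule and the D.1 nonresponse rule say follow-up, which could mean the outcome's own wave or the six-month survey. For scale, Figure A.3 shows (64 + 52)/(206 + 190) = 116/396 = 29.3% of those eligible with a completed follow-up at the July 22, 2024 data pull. This is interim, and contact windows may still have been open.

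**The case against.** The strongest reply has four parts.

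- **The instrument already screens.** A reader might infer that Attitudes has no relationship screen at all, because D.2 writes its condition for Behaviors only. The documents do not support that. After October 2023 the skip logic routes people without a committed partner past the Attitudes items too. Only the early respondents remain, and D.2 discloses that rule and its reason. This part stands.
- **Two of the timing rules have a benign reading.** D.2 speaks of time points for the construct in question, and D.1 lists the post-survey as a source of attrition and describes complete-case analysis outcome by outcome. A reader might infer that the plan deliberately discards six-week scores from six-month nonrespondents. The text does not settle that; it should simply say which wave is meant. The reply does not rescue the timing covariate or the change-score definition.
- **The D.3 sentence describes availability.** A reader might infer that it excludes people without a partner from the model. It states no exclusion, so that is inference. The contradiction with Table 6 remains.
- **Baseline status is a choice.** A.2 does not say when the relationship must be reported, and the items ask about a current partner, so status at the survey has some logic. But the skip question did not exist for early respondents. The ACS item is recorded before randomisation and is already planned as a covariate. The ACS categories do not match the skip question exactly and some people did not answer, so both need a stated rule.

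**Conclusion.** The point holds and should be corrected before analysis, at a level suited to exploratory outcomes. The early-respondent rule departs from the plan's own question, D.3 and Table 6 contradict each other, and the six-week Attitudes outcome is adjusted for something measured after it.

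The size is uncertain. About 22-27% of main-cohort post-surveys precede the switch if enrollment is even. The share without a partner in the scored Attitudes sample runs from about 0% to 24%. A reader might settle on the third row of the table (about 9-16%) as an estimate, but that row assumes that the same people are missing at both waves and that all of them lack a partner, and the documents say neither. Nor is 24% a ceiling, since more than 50% had no partner. The missing rate may be item-level, and the 50% describes ACS responders through grant year four, not early respondents specifically.

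For Behaviors the early share is probably small (0-3% of main-cohort follow-ups at six months). It would go too far to call that outcome untouched, given the pilot cohort and the July 2023 start in Figure A.3. The documents do not allow an estimate of bias from selecting on status after randomisation. The primary outcomes are unaffected.

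**What to change.** - **Sample.** Define it for both secondary questions by ACS relationship status at baseline, applied identically before and after October 2023. State how on-again off-again relationships (17% of those answering) and missing ACS status are handled. Keep the current D.2 rule as a sensitivity analysis.
- **Reporting.** Give relationship status and outcome availability at the outcome survey by arm, with a caveat that the skip logic leaves some post-randomisation selection.
- **Covariate.** Reconcile D.3 with Table 6: take relationship status from the ACS, delete the condition on status at follow-up, and drop the covariate if it is constant in the resulting sample.
- **Attitudes timing.** Define complete case and any change score as baseline plus post-survey, and use days from enrollment to post-survey as the timing covariate. State in D.1 and D.2 that nonresponse and complete-case rules apply at each outcome's own wave.

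The cost is plan wording; the ACS item and the post-survey date are already collected. The sample becomes smaller for outcomes already described as underpowered. The change cannot recover answers skipped by people who had no partner at the outcome survey.

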Wave 3 of data collection, which includes the local evaluation 6-month post-enrollment follow-up survey, is intended to be collected six months after program enrollment, with data collection efforts focused on five to seven months after program enrollment. However, the timing of the follow-up survey data collection can vary, with some participants taking the survey later than expected (e.g., an email with a survey link is opened and completed months after it was delivered) or earlier than expected (in the case of Franklin CBCF participants who complete their follow-up survey immediately upon release; see below). The tracking process typically begins at least 60 days prior to when a participant is due for a follow-up survey. This allows time for new contact attempts when email addresses are undeliverable and mailings are returned to the sender. The incarcerated population also tends to be a difficult population to get in touch with for various reasons. Someone just released from prison may be focusing on housing and employment needs or their contact information is outdated since they were enrolled into the program.

Waves 1 and 2 of all surveys are administered on paper with participants in person, due to technology restrictions in the prison facilities. Paper surveys are entered onto nFORM and Qualtrics (for the local evaluation surveys) within 72 hours of completion by RIDGE staff who have been certified in protecting human research participants. Paper surveys are securely transported by program staff to the RIDGE offices where they are entered and kept in locked storage.

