The process for follow-up data collection (Wave 3) differs from the other two waves. The MER survey tracking team begins attempts to contact study participants approximately five months after program enrollment using email and text messages as the primary contact methods. Participants are sent a QR code and hyperlink that directs them to the self-administered formatted follow-up survey accessed through Qualtrics. Participants can also complete the follow-up survey over the phone with a member of the MER survey tracking team if they prefer. If initial contact attempts are not successful, the survey tracking team will reach out to secondary contacts that participants have identified and provided contact information for during the study enrollment process. Contact attempts continue for 60 days (until 7 months after program enrollment), after which point the survey tracking team stops efforts to collect follow-up surveys. At this point, program staff are provided a list of participants that the tracking team is

unable to get in contact with. If program staff come in contact with any of the participants on the archived list, they will direct the participants to the follow-up survey. Otherwise, all tracking efforts are complete at that point. All participants who complete a follow-up survey receive a \$50 incentive.

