To increase follow-up response rates and with the approval of OFA, alternative follow-up data collection procedures were developed by the RIDGE and evaluation teams for one service site that enrolls most of the impact study participants at about 78%, Franklin CBCF. Many impact study participants from the Franklin CBCF service site go on to participate in a Department of Labor initiative immediately following their release from prison. As part of this initiative, participants are bussed from the Franklin CBCF to an American Jobs Center. TYRO Couples RCT participants who are part of this initiative are invited to complete a paper follow-up survey on the Thursday prior to the bus taking participants to the American Jobs Center the following Monday morning. Eligible participants who completed the survey will be handed a physical \$50 gift card upon boarding the bus. This follows guidelines of prisons where no monetary incentives can be administered on the premises. To be eligible for the follow-up survey, participants must have a signed consent form on file and have taken either the nFORM entrance survey or the local evaluation baseline survey. Evaluation staff will coordinate with program staff to ensure only those who are eligible for the follow-up survey are offered it. Paper surveys will be sealed in an envelope where they are given to a team member certified in protecting human research participants to enter the surveys into Qualtrics. Paper surveys are to be kept in locked storage at RIDGE offices and will be stored for a minimum of three years before being destroyed in accordance with IRB guidelines. This process is set to begin in May 2024.

Table 5. Key features of the data collection

Study group	Data source	Timing of data collection	Mode of data collection	Party responsible for data collection	Start and end date of data collection
Intervention (on-demand)	Survey Wave 1 (nFORM baseline and local evaluation baseline surveys)	Immediately following informed consent and randomization during orientation (within 1-2 weeks of enrollment)	In-person paper survey	RIDGE Staff	April 11, 2023 – November 30, 2024
	Survey Wave 2 (nFORM exit and local evaluation post-surveys)	Six weeks after program enrollment	In-person paper survey	RIDGE Staff	May 23, 2023 (or February 2023 for pilot cohort) – January 11, 2025

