	Survey Wave 3 (Local evaluation follow-up survey)	Six months after program enrollment; Between three to six months after program enrollment at Franklin CBCF	Online via a QR code or email link; over the phone; in person paper survey if in the eligible Franklin CBCF group	MER Staff or RIDGE facilitator if in the eligible Franklin CBCF group	October 2023 – May 31, 2025 for all locations aside from Franklin CBCF; For Franklin CBCF- May 2024- May 31, 2025

Study group	Data source	Timing of data collection	Mode of data collection	Party responsible for data collection	Start and end date of data collection
Counterfactual (in-person)	Survey Wave 1 (nFORM baseline and local evaluation baseline surveys)	Immediately following informed consent and randomization during orientation	In-person paper survey	RIDGE Staff	April 11, 2023 (or January 2023 for pilot cohort) - November 30, 2024
	Survey Wave 2 (nFORM exit and local evaluation post-surveys)	Six weeks after program enrollment, immediately following the last primary workshop session	In-person paper survey	RIDGE Staff	May 23, 2023 (or February 2023 for pilot cohort) – January 11, 2025
	Survey Wave 3 (Local evaluation follow-up survey)	Six months after program enrollment; Between three to six months after program enrollment at Franklin CBCF	Online via a QR code or email link; over the phone; in person paper survey if in the eligible Franklin CBCF group	MER Staff or RIDGE facilitator if in the eligible Franklin CBCF group	October 2023 – May 31, 2025; For Franklin CBCF- May 2024- May 31, 2025

3. CONSORT diagram

The CONSORT diagram for this impact study (where random assignment occurs after consent) can be found in the appendix to this plan. The data used to complete the CONSORT diagram were pulled on July 22, 2024.

D. Analysis

This section describes the plans for defining the analytic sample, assessing baseline equivalence, cleaning data, handling missing data, and addressing potential crossover and contamination. It also describes the analytic models for estimating program impacts and planned sensitivity analyses.

1. Data preparation

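### Both primary models condition on observed days to follow-up, a variable fixed only after assignment, and no planned analysis shows the arm effect without it

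*Combined protocol and SAP*

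**What the plan says.** Section D.3 (Modeling approach) sets one linear model for all outcomes: "The basic model for this impact evaluation will include a dummy variable for intervention group assignment", together with the baseline score. It then adds age, gender, race and the "number of days between program enrollment and follow-up survey completion" for all outcome analyses. Table 6 lists the same term: "Number of days between program enrollment date and date of follow-up survey completion to control for variation in survey timing". A facility indicator is only to be considered.

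On how the survey date arises, section C.2 (Data collection) says that "the timing of the follow-up survey data collection can vary, with some participants taking the survey later than expected" and others earlier. It explains why people are hard to reach: "Someone just released from prison may be focusing on housing and employment needs". For Franklin CBCF, with about 78% of the impact sample, it sets up an early route tied to a Department of Labor jobs initiative: "TYRO Couples RCT participants who are part of this initiative are invited to complete a paper follow-up survey", a few days before they are bussed to a jobs center. Table 5 puts Wave 3 at Franklin between three and six months after enrolment, against an intended window of five to seven months.

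Section C.2 also states that data collection process and timing do not depend on study condition.

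Section D.4 plans three sensitivity analyses. The one on timing repeats the analyses among people surveyed at five to seven months.

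**The concern.** A covariate fixed before assignment can improve precision without disturbing the randomised comparison. A covariate realised afterwards has no such guarantee. If arm influences it, and it shares unmeasured causes with the outcome, conditioning on it makes the arms differ in those causes.

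Days to follow-up is the only covariate in Table 6 that is not a baseline value. It is not pure administrative noise either. At the dominant site a short interval partly marks entry to a jobs programme, and employment attitudes is a primary outcome. The link from employment circumstances to timing therefore has some support in the plan. The link from arm to timing has not been shown.

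At stake is whether the reported arm effect on both primary outcomes can be read as the randomised contrast. The plan gives the reader no means of checking, because every planned model carries the term.

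**Working it through.** **1. Is there any planned model without the term?** Section D.3 applies it to all outcome analyses. In section D.4, the first two sensitivity analyses change how missing scale items are handled (a 70% threshold; mean imputation). The third repeats the same analyses in the five-to-seven-month subset, so it keeps the term and also selects participants on that same variable. The plan commits neither to a days-free model nor to a report of days by arm.

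**2. The plan's own sample size, as a yardstick.** Section C.1 gives a target of 768, or 384 per arm, with no alpha, power, effect size or SD, so the figure cannot be reproduced from stated inputs. Assuming two-sided 5% and 80% power, the detectable difference is (1.96 + 0.84) × √(2/384) = 2.80 × 0.0722 = 0.202 SD.

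**3. Bias formula.** Let *a* be the shift in mean days caused by arm, in within-arm SDs of days. Let *r* be the within-arm correlation of days with the outcome that comes from shared causes, after the baseline covariates. In a model with arm and days, the bias in the arm coefficient is −*a* × *r*, in residual SDs of the outcome. If *a* = 0 the bias is 0. Its direction depends on the signs of *a* and *r*.

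**4. Assumed inputs.** The documents give neither *a* nor *r*; both are taken as 0.1 to 0.3. To put *a* in days, assume surveys spread evenly from three to seven months (91 to 213 days): SD = 122/√12 = 35.2 days, so 0.1 to 0.3 SD is about 4 to 11 days. This spread leaves out surveys after seven months.

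**5. Results.** Formula against simulation (384 per arm, true effect zero, 4,000 runs per row, nominal two-sided 5%, no baseline score, so *r* stands for the residual correlation):

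| a | r | −a × r | Simulated bias | False-positive rate, days in | False-positive rate, days out |
|---|---|---|---|---|---|
| 0 | 0.3 | 0.000 | 0.000 | 0.054 | 0.050 |
| 0.1 | 0.1 | −0.010 | −0.010 | 0.056 | 0.052 |
| 0.2 | 0.2 | −0.040 | −0.041 | 0.093 | 0.053 |
| 0.3 | 0.3 | −0.090 | −0.091 | 0.263 | 0.046 |

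Against the yardstick, 0.010/0.202 = 5% and 0.090/0.202 = 45%. The low end is also small beside the standard error: 0.010/0.072 is about one-seventh.

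**6. Precision given up by dropping days.** If days explain 1% of residual variance, the standard error rises by 1/√0.99 − 1 = 0.5%; at 4%, by 1/√0.96 − 1 = 2.1%.

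**7. What the interim counts add.** The CONSORT figure shows 64/206 = 31.1% and 52/190 = 27.4% followed up (z = 0.81; arm labels not visible). That is no clear difference in response, and it says nothing about days to response.

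**The case against.** The strongest reply is that the necessary link is missing. Section C.2 fixes the same process and timing for both arms, and Table 5 gives both the same Wave 3 timing, modes and collectors. At Franklin the early date follows release and the bus schedule, which individual randomisation within cohorts should balance. This stands: no arm effect on timing is documented. It does not fully settle the matter, because the model uses actual days, which section C.2 says vary.

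Two stronger readings are tempting and should not be made.

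- A reader might take the Table 5 entry "MER Staff or RIDGE facilitator if in the eligible Franklin CBCF group" to mean that collection favours the in-person arm, since facilitators teach only there. But the entry is the same for both arms, facilitators meet everyone at orientation and announce the assignments (section C.1), and who collects a survey does not set its date.
- A reader might infer from "If program staff come in contact with any of the participants on the archived list, they will direct the participants to the follow-up survey" that very late surveys come through staff. This is one route only; section C.2's own example of lateness is an emailed link opened months afterwards.

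The employability link is also partly inferred. The plan gives no selection rule for the jobs initiative and does not relate days to attitude scores. The baseline score should absorb part of any such association, so the relevant *r* may be small.

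Finally, there is a case for adjusting. The question is impact at six months, while surveys run from about three months to beyond seven. If attitudes change with elapsed time and the arms differ in timing, the days-free contrast is off for that question by the arm shift times the causal slope. This stands as a reason to keep the adjusted model in the report. It is not a reason to have no other model.

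**Conclusion.** The concern holds in a limited form. Both primary models condition on a variable realised after assignment, at the main site that variable is tied to entry into a jobs initiative, and no planned analysis shows the arm contrast without it. The arm estimate can therefore be biased, but only if arm affects timing, which the documents do not show.

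A reader might go further and conclude that the primary estimates are biased, or that 0.01 to 0.09 SD is an estimate of the bias. Neither is supported. The range rests wholly on assumed values of *a* and *r*, the true size is unknown, and it is zero if *a* is zero. The five-to-seven-month analysis does not resolve the question, since it keeps the term and selects on it.

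The change is worth making because a model using only pre-assignment covariates is free of this particular bias whether or not arm affects timing, and costs very little.

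**What to change.** In section D.3 and Table 6:

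- Make the primary model days-free: arm, baseline score, age, gender, race, facility and randomisation cohort. Facility and cohort are both fixed at assignment; facility moves from optional to specified.
- Report the distribution of days to follow-up by arm.
- Keep the days-adjusted model as a named sensitivity analysis in section D.4, beside the five-to-seven-month analysis.

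A flag for enrolment cohorts under the May 2024 Franklin procedure would not serve as a timing covariate. That procedure applies at release, so people enrolled earlier but released later would be misclassified.

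The cost is a wording change, one further model run and a standard error about 0.5 to 2% larger if days explain 1 to 4% of residual variance. If the arms do differ in timing, the primary contrast will include that difference; the sensitivity model and the days-by-arm report would show it. Selection through non-response is a separate matter that this change does not address.
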